Finally, the FoodImage app, and its data collection methodology, integrates customizable notifications and reminders to remotely prompt participants to record data, resolve data collection problems, etc. These notifications and reminders utilize Ecological Momentary Assessment (EMA) methodology¹¹ to maximize data collection protocol adherence by reminding participants to capture and send food information at relevant times. This notification functionality of FoodImage can also be leveraged to communicate information about ongoing interventions and can facilitate adherence to dietary changes and strategies to reduce food waste.

Increasing household FV consumption while reducing food waste requires behavior to change in two overlapping domains, each of which has been the focus of considerable work^{7 12}. Current efforts to change household level behavior are often compartmentalized, focusing either on increasing FV consumption or reducing food waste, but not on the behaviors together. In doing so, existing interventions fail to consider the linkages between behaviors that occur in households and may affect positive change in one domain with negative or neutral impacts on the other domain (e.g., increase FV consumption but increase food waste or reducing food waste by limiting fresh FV consumption). Hence, it is essential to articulate any unintended consequences that existing programs present across these two domains and create interventions that simultaneously promote behavior change that advance both goals.

Methods

Study Design

We will conduct a randomized controlled trial (RCT) featuring two groups that both receive free boxes of FV. The box of fresh FV will contain about 40% fruit and 60% vegetables and be sufficient to meet 60 ±5% of the household's FV needs as recommended by USDA's MyPlate. The amount of FV provision will scale in proportion to the size of the household as is done with SNAP benefits (as noted earlier, it is estimated that ~20% of participants will actually be eligible for SNAP). The groups differ in the intervention provided, with the treatment group receiving a smart intervention to reduce food waste and replace consumption of less healthy foods with FV and the control group receiving an intensity-matched intervention focused on an unrelated topic (stress management).

Participants

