At Visit 1, participants will come to PBRC and will provide informed consent. Post consent, the participant's height, weight, and BMI will be measured and recorded. Participants will install and learn how to use the FoodImage app. They will complete a baseline questionnaire including questions about demographics, SNAP eligibility, and socioeconomic variables. They will also complete a Household Needs Survey to obtain the height, age, activity level and weight of household members as well as any allergies, intolerances, and food related restrictions in the household. They will also complete a Fruit and Vegetable Preference Survey (FV Preference Survey) to let researchers know which fruits and vegetables can be included in each household's box. If the participant begins to express fatigue or the PBRC employee performing the visit deems it necessary, the surveys can be sent to the participant via email through REDCap¹³. Participants should complete the surveys within 24 hours of Visit 1 and a PBRC employee will follow-up with the participant if the surveys are not completed during this time. If a mistake is made or questions are unintentionally omitted, a PBRC employee will call the participant within 24 hours to collect the remaining data and/or participants will fill out surveys at Visit 2. Participants will also receive instruction on how to conduct a fridge and cabinet cleanout and how to conduct a household Fruit Vegetable inventory. Following Visit 1, participants will collect data in a free-living environment over the course of approximately 1 week. To prepare for home data collection, participants will be asked to clean out their fridge, freezer and cabinets of any items that need to be discarded. After the cleanout is conducted, the participant will complete a video home inventory of all fruits and vegetables including fresh, frozen, & those otherwise preserved. This fruit and vegetable inventory will be conducted via a Microsoft Teams video call with a study staff member. This video call will be recorded and stored for data analysis purposes. During the call, the participant will perform the home Fruit and Vegetable Inventory guided by the study staff member; the study staff member will ask probing questions to ensure all fruits and vegetables have been shown. Following the

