call, the study staff member will complete data entry for the fruits and vegetables inventoried on the call. Participants will also complete baseline data collection using the FoodImage app to record food acquisition (Shop), food prep (Prep), intake (Eat) and waste (Toss) for approximately 3 (24 hour) days; ideally including 1 weekend date.

At Visit 2, participants will be randomized, as described in the analysis section, to one of two groups: A Food Waste & Substitution Group (Treatment Group) or a Stress Management Group (Control Group). Both Groups will receive their first fruit and vegetable box, will complete a lifestyle interview, and will receive their first group specific intervention visit.

Participants in the **treatment group** will meet individually with a trained coach who presents a set of materials that includes an introduction of food waste, ways that food waste can be reduced over time, and how to increase FV consumption by replacing consumption of less healthy foods with FV. The coach and participant then discuss the participant's lifestyle, including things like typical eating, shopping, prepping, storage, and meal habits. They also may discuss things like the number of people in the household, number of shopping trips, meal planning (or lack thereof), etc. The coach and participant will then tailor actions to most effectively reduce food waste and increase FV intake. In ensuing sessions, steps are made to follow up on plans and to introduce new plans to reduce food waste and increase fruit and vegetable intake. Between these in-person sessions, the interventionist will check in with the participant to follow-up on their progress. These check-ins can occur via phone, video chat, etc. To identify ways in which such interventions can be improved and to facilitate intervention fidelity and internal validity, some sessions with participants will be recorded. These recordings will be reviewed by the study team, namely Drs. [name], [name], and [name].

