Data from the FoodImage app will be prepared for analysis using methods detailed in [name] et al. (2020)¹. Briefly, images captured through the app are viewed by PBRC's nutrition staff who identify nutrient matches using Standard Reference (SR) 28 and the Food and Nutrient Database for Dietary Studies (FNDDS) 6.0¹⁴ (USDA 2020b)¹⁵ and estimate the mass of portions of food acquired, prepared, selected, consumed, returned, and discarded at each stage. Specifically, we will obtain mass (grams), energy (kilocalories), and macronutrients for shop, prep, eat, and toss occasions. The SR database provides inedible percentages. Furthermore, for all foods except raw meats where the SR database is used, we will obtain highly granular data. The FNDDS database translates whole food items into FPED values which converts each consumed food and beverage into the 37 USDA Food Patterns components¹⁶. The FPED values are used to assist in the quantification of diet quality (HEI) and to guide healthy food intake patterns (e.g., the 'five a day' campaign to promote FV consumption). The Food Patterns are measured as cup equivalents for fruits and vegetables. Thus, we can examine the number of servings of fruits, vegetables, dairy, grains, and proteins (each of the food groups) consumed. Also, we will examine diet quality in relation to the USDA Dietary Guidelines for Americans with the HEI¹⁷. During the two ≥ 3 -day intensive collection windows, participants record the source, reason and destination of all food waste on the app, which is attached to each data point. Receipts associated with food acquisition, which are collected for all 28 days, are processed via Optical Character Reader (OCR) with resulting price data checked for accuracy by human raters.

The method proposed by Pocock and Simon¹⁸ will be used for intervention assignment to minimize imbalance among factors that might be associated with outcomes of interest. Specifically, randomization will be adaptive according to the values of the Aitchison distance calculated using the following prioritized drivers of FV consumption and food waste: 1) the presence of children in the home vs. no children, 2) SNAP eligibility vs. being ineligible, and 3) the presence of a fruit tree and or garden at the home vs. the absence of these amenities. Greevy et al.¹⁹ the sample size required for achieving the same power is often reduced if factors associated with the outcomes are balanced among the intervention groups.

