 - b. FPED values, i.e. serving size, for food intake and consumption of FV including FV inventory, total FV acquisition, and total FV intake
 - c. Quantify baseline diet quality (i.e. food intake as assessed by the HEI)
- 2) Determine how the smart intervention altered:
 - a. Mass (grams), energy (kcal), and macronutrients (g and kcal) for household food waste levels, food purchasing patterns, food intake, and consumption of FV including FV inventory, total FV acquisition, and total FV intake
 - b. FPED values, i.e. serving size, for food intake and consumption of FV including FV inventory, total FV acquisition, and total FV intake
 - c. Quantify diet quality (i.e. food intake as assessed by the HEI)
 - d. Acquisition and intake of non-FV foods
 - e. The percent of household food waste that was FV

Secondary analysis objectives include assessing the demographic (e.g., age, education), household (SNAP eligibility, household size, beginning food inventories), and attitudinal factors (e.g., frugality, health and environmental consciousness) related to the primary analysis targets.

Power analysis

Power analysis was conducted for change in the primary outcome variable (grams [g] of food waste) from baseline to the end of the intervention to detect significant differences between treatment and control groups. Following the methods of our previous study, waste data will be summarized and analyzed by aggregating across measurement days. Based on weekly data from our previous study, the participants in the group receiving a smart food waste reduction intervention reduced their waste at meals by 331 g while the control group only reduced their waste by 33 g (298 g group difference), while the pooled standard deviation of the change in food waste between the control and treatment groups was 295 g, yielding an effect size of 1.01. The power to detect an effect size of 1.01 is 0.92 if there is no attrition (23 per group) and is 0.88 if attrition exceeds the 10% expectation (20 per group or 13% attrition). Given the power analysis is based upon an RCT that did not involve the provision of free FV, we expect effect sizes to be larger in the proposed study due to the presence of free FV, yielding even higher power than projected above.

Provisions to Monitor the Data to Ensure the Safety of Subjects

Adverse events will be monitored at each intervention visit. The PI and his co-investigators will review all data continuously to ensure the safety of each subject.

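### Household size, which sets the size of the free box and is known before randomisation, is left out of the primary comparison of change in raw grams of waste, at some cost in precision

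*Combined protocol and SAP*

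**What the plan says.** **Outcome.** The Power analysis section names the powered outcome: "Power analysis was conducted for change in the primary outcome variable (grams [g] of food waste) from baseline to the end of the intervention". On its handling it adds: "Following the methods of our previous study, waste data will be summarized and analyzed by aggregating across measurement days". No per-person scaling, model or covariate set is given. Objectives and Study Endpoints define waste at household level.

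**Box.** Under Study Design both arms receive a box "sufficient to meet 60 ±5% of the household's FV needs as recommended by USDA's MyPlate", and "The amount of FV provision will scale in proportion to the size of the household as is done with SNAP benefits". The first box is handed over at Visit 2, after baseline collection.

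**Household information.** At Visit 1 (Procedures): "They will also complete a Household Needs Survey to obtain the height, age, activity level and weight of household members". Assignment follows: "At Visit 2, participants will be randomized, as described in the analysis section, to one of two groups".

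**Balancing.** The Analysis section uses Pocock-Simon minimisation on three factors: "1) the presence of children in the home vs. no children", SNAP eligibility, and a fruit tree or garden. Household size is not one of them. Eligibility allows at most two children and sets no limit on adults.

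**Role of household size.** Study Endpoints lists it only among secondary factors to be related to the primary targets: "household (SNAP eligibility, household size, beginning food inventories".

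**Expected direction.** H1b predicts that free FV will raise waste in the control arm.

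**The concern.** A change score removes household differences that are stable over time. It cannot remove one that begins after baseline. The box is such an input: a four-person household receives far more produce than a one-person household, and neither had a box at baseline. If some of the box is wasted, as H1b expects, the change in grams will tend to be larger in larger households in either arm. Baseline waste, measured without the box, is only an indirect proxy for this.

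With 20 to 23 households per arm, that spread goes into the error term of the main contrast (H2c) unless size is in the model. Presence of children is a partial proxy: it does not separate one child from two, or one adult from several. The planning SD cannot contain box-driven spread, because the Power analysis section says the source trial gave no free FV. The same section argues that the box will enlarge the effect, but does not mention that a scaled box may also enlarge the SD.

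**Working it through.** **1. Inputs from the plan.** Group difference 331 − 33 = 298 g; SD of change 295 g; 23 per group without attrition, 20 with it; stated power 0.92 and 0.88. Alpha is not stated; I assume two-sided 0.05.

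**2. The plan's own figure.** Effect size 298/295 = 1.01. A two-sample t-test (noncentral t, noncentrality 1.01 × √(n/2)) gives 0.918 at 23 per group and 0.875 at 20. The stated power reproduces.

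**3. Adding size-driven spread.** Let k be the extra grams of waste change per additional person and s the SD of household size. The documents give neither, so the product k·s is an assumed range, taken on the same scale as the 295 g. With equal slopes in both arms:

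unadjusted SD = √(295² + (k·s)²)

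With size as a covariate the residual SD returns to 295 g and one degree of freedom is lost; power is then 0.875 at 20 per group and 0.917 at 23.

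| k·s (g) | SD (g) | Power unadjusted, n = 20 | Gain from adjustment | Power unadjusted, n = 23 | Gain |
|---|---|---|---|---|---|
| 60 | 301 | 0.862 | 1 point | 0.907 | 1 point |
| 120 | 318 | 0.822 | 5 points | 0.874 | 4 points |
| 150 | 331 | 0.792 | 8 points | 0.848 | 7 points |
| 180 | 346 | 0.757 | 12 points | 0.816 | 10 points |

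With s = 1.0 to 1.3 persons (assumed), k·s = 120 g means k of about 92 to 120 g per person.

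**4. Unequal slopes.** The intervention aims to cut waste, so it may flatten the slope in the treated arm. Suppose the treated slope is half the control slope and the difference is held at 298 g. A common-slope covariate then leaves a quarter of the control k·s in each arm (half the gap between the slopes). At 20 per group:

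- Control k·s = 120 g: unadjusted SD √(295² + (120² + 60²)/2) = 310 g, power 0.84; adjusted SD √(295² + 30²) = 297 g, power 0.87. Gain about 3 points.
- Control k·s = 180 g: unadjusted SD √(295² + (180² + 90²)/2) = 328 g, power 0.80; adjusted SD √(295² + 45²) = 298 g, power 0.87. Gain about 7 points.

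If the treated slope is zero, the gains are about 1 and 3 points.

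**5. Cost if size is irrelevant.** At 20 per group, losing one degree of freedom moves power from 0.8755 to 0.8750. Entering all five terms proposed below (size, baseline waste, three minimisation factors; 38 − 5 = 33 degrees of freedom), none of them prognostic, gives 0.873.

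**The case against.** The plan names no primary model at all, so the absence of household size is silence and not a decision to exclude it; the same could be said of baseline waste. Presence of children, a main driver of size, is the first balancing factor, and children are capped at two. The box may also enlarge the effect: with k·s = 120 g, a difference of 298 × 318.5/295 = 322 g would restore the planned power, and with 180 g, 349 g would. Units are a further difficulty. The 298 g and 295 g come from weekly data on waste at meals, whereas this trial records whole-household waste over about three days.

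Much of this stands. It means that the size of the loss is conjecture, and the effect and the SD may both rise. Balancing on children also helps. In a simulation with assumed household mixes, it cut the SD of the arm difference in mean size at 23 per group from about 0.28–0.32 to 0.21–0.23 persons, and children yes/no explained about 41–49% of the variance in size. If that factor were in the model, 180 g of size-driven spread would fall to 180 × √0.51 to 180 × √0.59, or 129 to 138 g. But the plan does not say that it will be in the model, and half or more of the spread would remain.

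None of this is a reason to leave out a covariate that is already collected and already sets the size of the box. The secondary analysis of household size is an association analysis and does not adjust H2c. Adding size to the primary model after the data are seen would be open to challenge.

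**Conclusion.** The point holds as a loss of precision that can be avoided at almost no cost. By the plan's own logic change in raw grams depends on household size, and size is only partly balanced and not adjusted for. At 20 per group, an assumed size-driven spread of 60 to 180 g puts unadjusted power at about 0.86 to 0.76. Adjustment recovers about 1 to 12 points with equal slopes, or about 3 to 7 points at 120 to 180 g if the treated slope is half the control slope. At the low end the matter is minor.

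A reader might infer more, in four ways that the documents do not support:

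- *That the comparison is biased.* Randomisation keeps it unbiased on average.
- *That chance imbalance in household size is a second harm.* It is part of the same variance term, and calculating it as for simple randomisation would ignore the minimisation on children.
- *That the trial is underpowered.* The documents quantify neither the added spread nor the larger effect they expect.
- *That adjustment would lift power above the stated figures.* That would need the 295 g already to contain size-driven spread. The box-driven part cannot be there, and the plan gives no figure for any other part.

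**What to change.** 1. In the Analysis section, prespecify the primary between-arm model for grams of food waste: follow-up waste on arm, baseline waste, the three minimisation factors, and household size as a continuous covariate. The household FV need already worked out to size the box would serve equally well. Use the value fixed before assignment; the Procedures allow missed survey items to be completed at Visit 2, so the value should be confirmed before the household is randomised.
2. Report grams per household member as a sensitivity analysis.
3. In the Power analysis section, state that the 295 g SD comes from a trial without boxes, so the box may raise the SD as well as the effect.

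The cost is a few sentences and one degree of freedom for household size. No new data, visits or participants are needed.

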A sample of up to 46 participants from the Baton Rouge, LA area will be enrolled. Due to the prolonged baseline assessment, enrollment is defined as having successfully completed the baseline assessments and having been randomized. Thus, more than 46 participants may begin the baseline period. We will enroll 46 participants. We anticipate ~10% attrition post-enrollment for about 20-21 completers per group and we are adequately powered with anticipated attrition.

Inclusion and Exclusion Criteria

- Inclusion criteria include:
 - Male or female, age 18-62 years
 - Body mass index (BMI) 18.5 – 50 kg/m², based on self-reported height and weight
 - Ownership of an iPhone, which the participant is willing to use for the study
 - Access to Apple ID, password, and email address and willing to use them in the course of the study
 - Performs a majority of household food shopping and preparation
 - If children are present in household, all children are between 6-18 years
 - Able to meet the schedule demands for the study
- Exclusion criteria include:
 - Not able to use an iPhone
 - Refusal or unable to use the smartphone app to collect data in free-living conditions
 - Households that purchase groceries less than 1 time per week
 - More than 2 children living in the household
 - Pennington Biomedical Research Center employee
 - Unwilling to sign consent to use web screener questions for data set and analysis.

Recruitment

Participant recruitment will be completed by Pennington Biomedical's recruitment core. Because most FV subsidy policies and programs target populations receiving SNAP, we will include recruitment at local food pantries to ensure an oversampling of participants who are likely SNAP eligible or recipients (target ~20% of participants). During the recruitment Web Screener, we will ask the participants the following 6 Food Insecurity screening questions:

1. In the last 12 months, did you ever eat less than you felt you should because there wasn't enough money for food?
--

2. In the last 12 months, were you ever hungry but didn't eat because you couldn't afford enough food?
--

3. In the last 12 months, did you ever cut the size of your meals or skip meals because there wasn't enough money for food?
4. In the last 12 months have you or other members of your household made a statement like, "The food that I bought just didn't last, and I didn't have money to get more."

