16-23*	Week* following V4	Interventionist will check in with ppt goals and will send group specific nudges via participant's preferred form of communication between V4 and V5.
16-23*	Week* following V4	Follow Up Data Collection Use FoodImage to record food acquisition (Shop), food prep (Prep), intake (Eat) and waste (Toss). • For approximately 3 (24 hour) days (ideally including 1 weekend date) use FoodImage to record all food acquisition (Shop), food prep (Prep), intake (Eat) and waste (Toss).
24*	Day before* V5	Conduct a home inventory of all Fruits & Vegetables (fresh, frozen, or otherwise preserved) via Microsoft Teams Call with a study staff member.
25*	Visit 5 ~ +7* days from V4 (~ 1 hour)	Visit PBRC to: 
 • Complete exit survey and review ending home Fruit & Vegetable inventory. • Measure Height, Weight & BMI.

*All Study Days and Visit Timing are approximate. The exact day of a study procedure or appointment may vary slightly due to changes in subject or research facility schedule.

Analysis

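### The stated power of 0.92 / 0.88 is derived for weekly waste at meals and is not shown to apply to this trial's outcome, household waste over windows of about 3 days

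*Combined protocol and SAP*

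**What the plan says.** The Power analysis section names the outcome: "Power analysis was conducted for change in the primary outcome variable (grams [g] of food waste) from baseline to the end of the intervention". The inputs come from an earlier trial: "Based on weekly data from our previous study, the participants in the group receiving a smart food waste reduction intervention reduced their waste at meals". The reduction given for that arm is 331 g. For the other arm the section says: "while the control group only reduced their waste by 33 g (298 g group difference". The pooled SD of the "change in food waste between the control and treatment groups was 295 g, yielding an effect size of 1.01". From this it concludes: "The power to detect an effect size of 1.01 is 0.92 if there is no attrition (23 per group) and is 0.88" with 20 per group. It adds that the earlier trial did not provide free fruit and vegetables (FV), and on that basis: "we expect effect sizes to be larger in the proposed study due to the presence of free FV, yielding even higher power than projected above".

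The Participants section expects "about 20-21 completers per group and we are adequately powered with anticipated attrition". The Study Endpoints section also says that power is sufficient for the primary objectives.

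The measurement plan is in Procedures, Schedule of Procedures and Analysis. Intensive recording is limited to two windows, one before randomization and one after Visit 4. The instruction for each is: "For approximately 3 (24 hour) days (ideally including 1 weekend date) use FoodImage to record all food acquisition", together with preparation, intake and discarded food. The Analysis section describes the windows as at least 3 days and says that all food waste is logged in them. After randomization, storage clean-out waste (Toss) is also recorded continuously. The Objectives and Study Endpoints sections frame the outcome as household food waste, not waste at meals.

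**The concern.** The effect size and the trial's outcome differ in two respects.

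- **Window.** The inputs are weekly. The trial records preparation and eating waste for about 3 days per period.
- **Scope.** The inputs are waste at meals. The trial counts household waste, which adds preparation and storage clean-out waste.

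The protocol offers no conversion for either. A standardized effect does not carry over unchanged when the outcome is measured over fewer days or from more sources, because the mean difference and the SD need not change by the same factor.

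This is the only justification given for 46 participants. If power for the outcome as measured is well below the stated level, a non-significant result says less about the intervention than a reader relying on 0.88 to 0.92 would assume.

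**Working it through.** **Inputs from the protocol.** Difference 331 − 33 = 298 g; SD of change 295 g; 23 per group, or 20 after attrition. Alpha and sidedness are not stated with the power figures. I take two-sided 0.05, which reproduces both figures; one-sided 0.05 gives 0.958 and 0.932 and does not.

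**Step 1: reproduce the stated power.** d = 298/295 = 1.010. For a two-sample t-test, the degrees of freedom are 2n − 2 and the noncentrality is d·√(n/2).

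- n = 23: noncentrality 1.010 × √11.5 = 3.43, power 0.918 (stated 0.92).
- n = 20: noncentrality 1.010 × √10 = 3.19, power 0.875 (stated 0.88).

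The arithmetic is right for these inputs.

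**Step 2: effect of the window alone.** Assumptions: the weekly figures cover seven recorded days, and the effect is proportional to days. The 3-day difference is then 298 × 3/7 = 127.7 g. Let r be the share of the weekly change variance that is day-to-day noise. The protocol does not give r, so it is shown as a range. The stable part of the SD scales by 3/7 and the noise part by √(3/7):

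SD over 3 days = 295 × √[(1 − r) × 9/49 + r × 3/7]

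d over 3 days = 127.7 / SD = 1.010 / √(1 + 4r/3)

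| r | SD over 3 days (g) | d | Power, 23 per group | Power, 20 per group |
|---|---|---|---|---|
| 0 | 126 | 1.01 | 0.92 | 0.88 |
| 0.25 | 146 | 0.87 | 0.83 | 0.77 |
| 0.5 | 163 | 0.78 | 0.74 | 0.67 |
| 1 | 193 | 0.66 | 0.59 | 0.53 |

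Here r is a share of variance, not of SD: noise with half the total SD corresponds to r = 0.25. Power falls below 0.80 once r exceeds about 0.18 at 20 per group, or about 0.32 at 23 per group.

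**Step 3: effect of scope alone.** The protocol gives no SD for household waste. Holding the gram effect at 298 g and varying the SD (assumed multipliers):

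| SD multiplier | d | Power, 23 per group | Power, 20 per group |
|---|---|---|---|
| 0.9 | 1.12 | 0.96 | 0.93 |
| 1.25 | 0.81 | 0.76 | 0.70 |
| 1.5 | 0.67 | 0.61 | 0.55 |

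If the added streams raise the effect and the SD by the same factor, d and power do not change.

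**Step 4: effect of a larger difference.** A 1.25-fold effect at r = 0.5 gives d = 1.25 × 0.782 = 0.98 and power 0.90/0.85. Fully offsetting r = 1 needs an effect √(7/3) = 1.53 times as large. In the other direction, r = 1 combined with an SD multiplier of 1.5 gives d = 0.44 and power 0.31/0.27.

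**The case against.** The strongest reply has four parts.

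- **The stated power is computed correctly, and the documents do not show that it is wrong for this trial.** This stands. A reader might infer that the design lacks the stated power, or that power is near a coin toss. The documents do not support that. They give neither the day-to-day variance nor an SD for 3-day household waste, and at r = 0 the stated figures survive the shorter window.
- **The meaning of weekly is unclear.** The section says that it follows the earlier study's methods and aggregates over measurement days. If that study recorded fewer than seven days and expressed the result per week, the 3/7 scaling overstates the penalty. The current window may also exceed 3 days. This stands as a limit on Step 2. It does not remove the difference in scope.
- **Free FV may widen the difference between arms.** This is plausible: more perishable food gives a waste-reduction intervention more to act on, and provision to both arms does not defeat the argument. But no figure supports it. Hypothesis H1b expects free FV to raise control-arm waste, and the SD could rise with it.
- **The intervention also targets storage and preparation.** The coaching covers inventory, planning, preparing and storing, so assuming no added effect from those streams is unfavourable to the trial. This stands, and it is why the scope change has no known direction.

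Continuous Toss recording does not close the gap. It starts only after randomization, so the baseline half of the change score still rests on about 3 days, and preparation and eating waste are scheduled only in the two windows. Participants also clean out storage before the baseline window, and no matching clean-out is described before follow-up. An SD for waste at meals would not reflect that difference.

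**Conclusion.** The point holds as a failure of derivation, not of calculation. The power is worked out for one measure and stated for another, without a bridge. Under the Step 2 assumptions a 3-day window can only keep or lower d, and 0.92/0.88 hold only if household waste has no day-to-day variation. A moderate noise share is enough to take power below 0.80. The size of any loss depends on r, on how the earlier weekly data were collected, and on how effect and SD change with scope and free FV, none of which the protocol reports.

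A reader might take the r = 0 to r = 1 figures as limits on the true power. They are not: they exclude any larger effect and any change in SD from scope, and Step 4 shows values outside them on the low side.

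The passage is wrong as written, because the stated power was not derived for the trial's own endpoint. It should be fixed. Nothing here requires a different sample size.

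**What to change.** Keep N = 46 and change the following.

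1. Define the primary outcome exactly: which waste streams count (preparation, eating, storage clean-out), how many days per period, and how post-randomization Toss records outside the window are treated.
2. Say what weekly means in the earlier data: seven recorded days, or fewer days scaled up.
3. Recompute the difference and SD of change for that outcome from the earlier data where they allow, using 3-day subsets and matching stages. If those data contain only waste at meals, they cannot supply an SD for all stages, and the protocol should say so.
4. Where recomputation is not possible, replace 0.92/0.88 with a sensitivity table over window, SD and effect size, labelled as assumption-based and not as a bound. State alpha and sidedness.
5. Delete or qualify the closing claim in Power analysis of still higher power, and qualify the statements of adequate power in Participants and Study Endpoints.

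The cost is a short re-analysis of the earlier study's data, some protocol wording, and probably a less favourable stated power.
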